3.3.5 Medical History

Medical History will be tabulated by system organ class and preferred terms using MedDRA coded terms.

Migraine History including age at diagnosis, the average number of headache days, migraine days, and migraine attacks per 28 day period in the 3 months prior to screening, suffers from aura, medication overuse headache diagnosis, length of chronic migraine history, as well as the timing of the start of migraines in relation to puberty/ menarche and hormone migraine history for females will be summarized in a table.

3.3.6 Clinical Trial Treatment

Total volume infused, number of infusions and reason for dose interruption will be listed as well as summarized in a table.

3.4 *Efficacy Analyses*

The secondary endpoints of patient reported outcomes (PROs) will be summarized with descriptive statistics by time point. These summary measures will be based upon the observed results and where appropriate the change from baseline results. The denominator for percentages will be the total number of PROs collected at each visit since not all subjects will complete PROs at all visits.

3.4.1 Most Bothersome Symptom (MBS)

The change from baseline will be summarized for MBS using the Safety Population at each scheduled visit.

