10.2.5. Questionnaires

Questionnaires should be administered to subjects in the order listed below at the time points specified in the Schedule of Events in [Section 2](#):

1. Columbia-Suicide Severity Rating Scale (C-SSRS)
2. Most Bothersome Symptom (MBS)
3. Patient Global Impression of Change (PGIC)
4. Short-Form Health Survey (SF-36)
5. Health-Related Quality of Life (EQ-5D-5L)
6. Headache Impact Test (HIT-6)
7. The Migraine Disability Assessment (MIDAS)

All questionnaires should be administered prior to dosing at dosing visits. Protocol number, subject number and date and time of administration must be captured on all questionnaires. All questionnaires completed by subjects must be reviewed for completeness and clarity by site staff prior to the subject leaving the clinic. The subject should be asked to complete any unanswered questions.

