10.2.5.2. Most Bothersome Symptom (MBS)

The Investigator will verbally obtain the most bothersome symptom associated with the subject’s migraines during the screening visit. The most bothersome symptom will be captured in the eCRF and may include nausea, vomiting, sensitivity to light, sensitivity to sound, mental cloudiness, fatigue, pain with activity, mood changes, or other migraine related symptom.

At each subsequent visit, the site staff will provide the questionnaire along with the other subject-completed questionnaires listed in [Section 10.2.5](#).

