15.7. Most Bothersome Symptom (MBS)

Most Bothersome Symptom (MBS)

This section to be completed by site staff at each visit, Screening through Week 56, or ET

Protocol: ALD403-CLIN-013 Subject #: _____ Visit Date: _____

Visit (please check one):

Screen Day 0 Week 4 Week 8 Week 12
 Week 24 Week 36 Week 48 Week 56 or ET

Most Bothersome Symptom (as noted by subject at screening visit): _____

This section to be completed by subject at each visit, Day 0 through Week 56, or ET

Since beginning this study, how would you describe the change (if any) in your most bothersome symptom? Choose ONE.

____ Very Much Improved
____ Much Improved
____ Minimally Improved
____ No Change
____ Minimally Worse
____ Much Worse
____ Very Much Worse

Version Date: 16 SEP 2016

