2.2.1 Questionnaires

Patient Global Impression of Change (PGIC)

The PGIC includes a single question concerning the subject's impression of the change in their disease status since the start of the study. Seven responses are possible: Very Much Improved, Much Improved, Minimally Improved, No Change, Minimally Worse, Much Worse, Very Much Worse.

SF-36 Health Survey (SF-36 v2.0)

The SF-36 v2.0 is a health survey containing 36 questions consisting of eight scaled scores to measure quality of life over the past 4 weeks. The eight sections measured are vitality, physical functioning, bodily pain, general health perceptions, physical role functioning, emotional role functioning, social role functioning, and mental health. Scoring software utilizing the 2016 norm-based scoring algorithm will be used to calculate the scaled score for each of the eight sections.

EQ-5D-5L

The EQ-5D-5L is a descriptive system of health-related quality of life states consisting of five dimensions/questions (mobility, self-care, usual activities, pain/discomfort, anxiety/depression) each of which can take one of five responses. The responses record five levels of severity (no problems/slight problems/moderate problems/severe problems/extreme problems) within a particular EQ-5D dimension. The EQ-5D-5L additionally includes a VAS scale. Each item will be summarized separately.

Headache Impact Test (HIT-6 v1.0)

The Headache Impact Test (HIT) is a tool used to measure the impact and effect on the ability to function normal in daily life when a headache occurs. The HIT is a 6 question, Likert-type, self-

reporting questionnaire with responses ranging from “Never” to “Always” with the following response scores: Never=6, Rarely=8, Sometimes=10, Very Often=11, Always=13. The total score for the HIT is the sum of each response score and will be treated as missing if the response is missing for one or more questions. The HIT total score ranges from 36 to 78, with score ranges having the following life impact:

Score Range	Life Impact
>= 60	Severe
56-59	Substantial
50-55	Some
<= 49	Little to None

Most Bothersome Symptom (MBS)

At screening subjects will identify migraine related symptom that is most bothersome for them. Subjects will be asked to rate the improvement in this symptom from screening on a seven-point scale identical to the scale used for the PGIC.

The Migraine Disability Assessment (MIDAS)

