3.2 Definition of Baseline

The baseline assessment will be the latest available valid measurement taken prior to the administration of Investigational Product. This will generally be Day 0.

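### SAP 3.4.1 plans a change from baseline for the Most Bothersome Symptom, but the item is already a change rating and its only possible baseline is another change rating

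*SAP*

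**What the plan says.** SAP 3.4.1 consists of one sentence: "The change from baseline will be summarized for MBS using the Safety Population at each scheduled visit". It gives no coding, no summary of actual values and no shift table.

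The item is described in two places. SAP 2.2.1 says: "Subjects will be asked to rate the improvement in this symptom from screening on a seven-point" scale, the same scale as the PGIC. The form in Protocol 15.7 asks: "Since beginning this study, how would you describe the change (if any) in your most bothersome symptom". Its subject section carries the instruction "This section to be completed by subject at each visit, Day 0 through Week 56, or ET".

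At screening, only the identity of the symptom is taken. Protocol 10.2.5.2 says: "The Investigator will verbally obtain the most bothersome symptom". No severity is recorded then or later.

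On timing, Protocol 10.2.5 says: "All questionnaires should be administered prior to dosing at dosing visits". On baseline, SAP 3.2 says: "The baseline assessment will be the latest available valid measurement taken prior to the administration of Investigational Product", and adds: "This will generally be Day 0".

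**The concern.** A change from baseline needs a state measured at two times. MBS has no measured state. Each answer is already a comparison with screening or the start of the study, and the earliest answer is given on Day 0 before any drug. Under the SAP's own definition of baseline, the MBS summary becomes a comparison of two change ratings on a bounded ordinal scale with no stated scoring.

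At stake is the readability of one listed patient-reported outcome. A programmer following the SAP would either produce a difference that is hard to interpret or have to guess that the rating itself was meant. Subjects who missed the Day 0 rating would also drop out of the change summary, even with complete later ratings.

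**Working it through.** The plan gives no figure on this point, so there is none to reproduce. The check sets the definitions side by side and then enumerates what the literal rule would yield.

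**Step 1: what the baseline would be.**
- Screening gives a symptom name and no rating (Protocol 10.2.5.2). The subject's part of the form starts on Day 0 (Protocol 15.7).
- Both schedules of events mark MBS on Day 0. The MBS row has no pre-dose footnote, but Protocol 10.2.5 puts every questionnaire before the infusion.
- SAP 3.2 takes the last valid pre-dose measurement. For MBS, only the Day 0 change rating qualifies. If it is missing, there is no baseline.

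**Step 2: how the SAP words its neighbours.**

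| SAP section | Instrument | What is summarised |
|---|---|---|
| 3.4.1 | MBS | Change from baseline only |
| 3.4.2, 3.4.5, 3.4.6 | SF-36, HIT-6, MIDAS | Actual score and change from baseline |
| 3.4.3 | EQ-5D-5L | Change from baseline, with a shift table per item |
| 3.4.4 | PGIC (same seven categories) | The change rating itself, with no reference to baseline |

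In 3.4.3 the same phrase means a comparison with the baseline value. In 3.4.4, where the item is a change rating like MBS, the SAP does not mention baseline.

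**Step 3: what a literal difference gives.** The documents state no coding. Assume +3 for Very Much Improved, 0 for No Change and -3 for Very Much Worse. Let *d* be the Day 0 rating, *t* the later rating and D = *t* - *d*.
- There are 7 x 7 = 49 possible pairs. They collapse to 13 values of D, from -6 to +6.
- D = 0 arises from 7 different pairs. Very Much Improved twice gives 3 - 3 = 0, and No Change twice gives 0 - 0 = 0.
- The attainable range is (-3 - *d*) to (3 - *d*), so it depends on the Day 0 answer: -3 to +3 for *d* = 0, -4 to +2 for *d* = +1, and -6 to 0 for *d* = +3.
- If *d* = 0, then D = *t*, and the difference is the rating itself.

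**Step 4: size of the shift in the mean.** Mean(D) = mean(*t*) - mean(*d*). Suppose a share *s* answers Minimally Improved on Day 0 (*d* = +1) and the rest answer No Change. Then mean(*d*) = *s* x 1, and mean(D) lies *s* below the mean rating at every later visit.

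| Assumed share *s* | Mean(D) - mean(*t*) |
|---|---|
| 0% | 0 |
| 10% | -0.1 |
| 20% | -0.2 |
| 30% | -0.3 |
| 50% | -0.5 |

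The documents give no basis for choosing *s*. Screening falls only 11 to 14 days before Day 0.

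**The case against.** The strongest reply is that the sentence may simply name the rating. The item asks about change, so change from baseline could be loose shorthand for the answer given. SAP 3.4 bases the outcome summaries on observed results, with change from baseline only where appropriate. Protocol 13.4 calls for frequencies and percentages of categorical variables and for results at each time point. On that view the seven categories will be tabulated anyway.

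Much of this stands. The observed rating is arguably already covered, and subtraction is not certainly what was intended. But baseline is a defined term in the SAP, 3.4.3 uses the phrase for a true comparison, and 3.4.4 avoids it for the matching item. Even on the loose reading the anchor is wrong, because baseline is generally Day 0 while the form refers to the start of the study and SAP 2.2.1 to screening.

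A reader might go further and infer one of three things, none of which the documents support.
- *That the difference has no clinical meaning.* Both ratings share one anchor, so their difference roughly approximates change since Day 0. Minimally Worse before dosing and No Change later does suggest improvement since Day 0.
- *That subtracting Day 0 cannot add information.* It does nothing when Day 0 is No Change, but that says nothing about the other cases.
- *That the result cannot be set beside the PGIC.* The PGIC form in Protocol 15.6 asks about change since first receiving study drug. The raw ratings already have different anchors, and netting out Day 0 would, if anything, move MBS towards the PGIC anchor.

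**Conclusion.** SAP 3.4.1 is wrong as written, with low impact. Applied with the SAP's own baseline, it compares two ordinal change ratings, gives the same score to quite different response pairs, and leaves subjects without a Day 0 rating with no change value. Read loosely, it gives the wrong reference point.

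The distortion is nil if all subjects answer No Change on Day 0 and grows with the share who do not. The mean shift of 0.1 to 0.3 category rests on an assumed +3 to -3 coding and an assumed 10% to 30% answering Minimally Improved on Day 0, with the rest answering No Change.

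MBS is one of six descriptive patient-reported outcomes in an open-label safety trial. The planned t-tests cover only SF-36, HIT-6 and MIDAS, and the sample size does not depend on MBS. No test, error rate or safety conclusion is affected.

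**What to change.** Replace SAP 3.4.1 with: *The seven MBS response categories will be summarised by number and percentage at each scheduled visit. No change from baseline is calculated. The Day 0 response is shown separately as a pre-treatment rating.*

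State one reference point for the rating (screening/start of study) wherever it is described, and note that it differs from the PGIC form, which refers to first study drug. No responder threshold needs to be added.

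The cost is one paragraph of SAP text and one table shell. No new data are needed, and no sample size, power or alpha changes.

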3.4.2 Short-Form Health Survey (SF-36 v 2.0)

The actual score and change from baseline in each of the eight sections will be summarized using the Safety Population at each scheduled visit using descriptive statistics. Testing of the change from baseline results will be performed at Weeks 12, 24, 36, 48, 60, 72, 84 and Week 104. T-tests will be performed for the change in the Mental Component and Physical Component scores. Scoring software utilizing the 2016 norm-based scoring algorithm will be used to calculate the actual score for each of the eight sections.

3.4.3 Health-Related Quality of Life (EQ-5D-5L)

The change from baseline will be summarized separately for each EQ-5D-5L item using the Safety Population at each scheduled visit. A shift from baseline to each scheduled visit will be tabulated for each item.

3.4.4 Patient Global Impression of Change (PGIC)

The change in disease status since the start of the study will be summarized for PGIC using the Safety Population at each scheduled visit.

3.4.5 Headache Impact Test (HIT-6)

The actual score and change from baseline in the total score will be summarized using the Safety Population at each scheduled visit. A shift from baseline to each scheduled visit will be tabulated. Testing of the change from baseline results will be performed at Weeks 12, 24, 36, 48, 60, 72, 84 and Week 104. T-tests will be performed based upon the change in total score.

3.4.6 The Migraine Disability Assessment (MIDAS)

The actual score and change from baseline in the total score will be summarized using the Safety Population at each scheduled visit. A shift from baseline to each scheduled visit will be tabulated. Testing of the change from baseline results will be performed at Weeks 12, 24, 36, 48, 60, 72, 84 and Week 104. T-tests will be performed based upon the change in total score.

3.5 Pharmacokinetic Analyses

The concentrations of Free ALD403 will be measured in plasma from all ALD403-treated subjects using validated assay methods. The PK analysis will include evaluations of concentration-time profiles for Free ALD403 at the following times: pre-dose on Day 0, immediately post-dose (within 15 minutes of end of infusion) and Weeks 2, 4, 8, 12 (pre-dose), 24 (pre-dose), 36 (pre-dose), 48 (pre-dose), 72 (pre-dose) and 104 or ET.

The concentrations of Free ALD403 will be listed and summarized by time point and descriptive statistics will be provided. In this analysis, concentrations below the lower limit of quantification (LLOQ) will be set to zero.

Plots of the individual concentrations of ALD403 will be presented over time (linear and log scales). Plots of the mean or median concentration will be presented over time (linear and log scales). When the scale is linear, concentrations below the lower limit of quantification will be set to zero. In the log-scaled figures, concentrations below the LLOQ will be imputed as LLOQ/2. A separate PK analysis plan with additional analyses will be created.

Population pharmacokinetic analysis will be performed, outside of this analysis plan, on the results for ALD403 concentrations obtained during this study in combination with the results from other studies of ALD403 in normal subjects and migraine patients.

3.6 Analysis of Safety Endpoints

3.6.1 Adverse Events

Adverse events are collected from the time of Informed Consent through the final subject visit. The incidence of all AEs and study drug-related AEs will be tabulated. These AEs will be classified by system organ class and preferred term using the MedDRA. For incidence reporting, if a subject reported more than 1 AE that was coded to the same preferred term/system organ class, the subject will be counted only once for that specific preferred term/system organ class. Events recorded between the time the informed consent is signed and the first Investigational Product administration will be listed.

A treatment-emergent AE (TEAE) is an AE with a start date and time on or after the date and time of the initial treatment.

For the purpose of inclusion in TEAE tables, incomplete AE onset and end dates will be imputed as follows:

Missing onset dates (where UK and UKN indicate unknown or missing day and month respectively):

- **UK-MMM-YYYY:** If the month and year are different from the month and year of the first dose of trial drug, assume 01-MMM-YYYY. If the month and year are the same as the first dose of trial drug month and year, and the end date (after any imputation) is on or after the first dose of trial drug, then assume the date of the first dose of trial drug. If the month and year are the same as the first dose of trial drug month, and year and the end date (after any imputation) is prior to the first dose of trial drug, then assume the end date for the onset date.
- **DD-UKN-YYYY/UK-UKN-YYYY:** If the year is different from the year of first dose of trial drug, assume 01-JAN-YYYY of the collected year. If the year is the same as the first dose of trial drug year, and the end date (after any imputation) is on or after the first dose of trial drug, then assume the date of the first dose of trial drug. If the year is the same as the first dose of trial drug, and the end date (after any imputation) is prior to the first dose of trial drug, then assume the end date for the onset date.

Missing end dates (where UK and UKN indicate unknown or missing day and month respectively):

- **UK-MMM-YYYY:** Assume the last day of the month;
- **DD-UKN-YYYY/UK-UKN-YYYY:** Assume 31-DEC-YYYY.

An overview of AEs, which includes subject incidence of TEAEs, study drug-related TEAEs, serious TEAEs, TEAEs leading to treatment withdrawal, TEAEs leading to treatment interruption, TEAEs leading to discontinuation and deaths will be presented.

The subject incidence of TEAEs and study drug-related TEAEs will be summarized by system organ class and preferred term.

Treatment-emergent AEs will also be summarized in a table by severity. For TEAEs presented by severity, the worst severity for each event during the clinical trial will be presented for each subject.

All AEs will be presented as a listing by subject. This listing will include the duration of the AE.

3.6.2 Deaths, Serious Adverse Events and Other Significant Adverse Events

3.6.2.1 Adverse events of special interest

Adverse events of special interest include the following and additional PTs to be determined at time of database lock;

Hypersensitivity and Anaphylactic Events

A subset of adverse events with a MedDRA coded SOC of Immune system disorders and PTs of Hypersensitivity, Anaphylactic reaction and Anaphylactoid reaction.

Events Associated with CSSRS

A subset of adverse events with a MedDRA coded SOC of Psychiatric disorders and PTs of Suicidal behavior, Suicidal ideation, Suicidal attempt and Self injurious behavior.

Cardiovascular Events

A subset of adverse events with a MedDRA coded SOC of Cardiac disorders and PTs of Atrial fibrillation, Bradycardia, chest pressure, Palpitations, Sinus bradycardia, Sinus tachycardia and Tachycardia.

A subset of adverse events with a MedDRA coded SOC of Investigations and PTs of Blood pressure increase, Blood pressure systolic increase, Elevated blood pressure, Heart rate increased, Heart rate decreased, Heart rate irregular, Electrocardiogram abnormal, Electrocardiogram Q wave abnormal, Electrocardiogram QT interval abnormal, and Electrocardiogram QT prolonged.

A subset of adverse events with a MedDRA coded SOC of Nervous system disorders and PTs of Seizure and Syncope.

A subset of adverse events with a MedDRA coded SOC of Vascular disorders and PTs of Flushing, Hot flush, Hypertension, Hypotension and Ischemia.

Hepatic Events

A subset of adverse events with a MedDRA coded SOC of Investigations and PTs of Alanine aminotransferase increased, Aspartate aminotransferase increased, Bilirubin increase, Hepatic enzyme increased, Liver function test abnormal, and Transaminases increased.

Events Associated with Study Drug Infusion

A subset of adverse events within one week of dosing with a MedDRA coded SOC of Skin and subcutaneous tissue disorders and PTs of Dermatitis bullous, Pruritus, Pruritus generalized, Rash, Rash macular, Rash macular-papular, Rash papular, Rash pruritic and Urticaria.

A subset of adverse events within one week of dosing with a MedDRA coded SOC of General disorders and administration site conditions and PTs of Infusion site erythema, Infusion site extravasation, Infusion site pain, Infusion site paresthesia, Infusion site pruritus, Infusion site rash, Infusion site reaction, and Infusion site swelling.

Adverse Event of Interest Analysis

The adverse events of special interest will be summarized and listed in the following categories:

- AESIs by system organ class and preferred term.
- AESIs by system organ class, preferred term, maximum severity, relationship to study drug and infusion interruption status.
- AESIs with action taken of study drug discontinuation by system organ class and preferred term
- AESIs assessed as serious by system organ class and preferred term.

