Central to this model of migraine is calcitonin gene-related peptide (CGRP). CGRP is one of the most abundant peptides in the human body and is produced in both peripheral and central neurons. It is abundant in trigeminal neurons and when released is involved in the vasodilation, inflammatory cascade, and pain transmission associated with migraine. In both peripheral and central pain pathways CGRP is associated with pain transmission and neuronal sensitization.⁹ Intravenous (IV) infusions of CGRP can cause a migraine-like headache in susceptible individuals with migraine.¹⁰ In addition, many pharmacological agents used as acute or prophylactic treatment of migraine are known to inhibit CGRP. Thus, CGRP is an attractive target for development of novel migraine pharmacology.

Currently the pharmacological treatment of migraine can be divided into acute treatment, that is, medications designed to reverse a migraine after it is initiated and preventive treatment that is designed to protect the nervous system from generating migraine. Acute treatments are used intermittently only as needed to stop an attack while preventative treatments are used on a sustained basis for periods of months to years. Acute treatment while generally quite effective can worsen the severity and frequency of migraine when used too frequently, a condition called medication overuse headache (MOH).⁴ MOH is common in populations with frequent episodic and chronic migraine.¹¹

Numerous medications are used to prevent migraine but to date none have been designed specifically for migraine. These commonly include tricyclic antidepressants, beta-blockers, and certain anticonvulsants. It is estimated that 45% of adults with frequent episodic migraine and virtually all with chronic migraine would benefit from effective preventive medications yet only an estimated 12% of this population are currently using a migraine preventive.¹ In large measure, this is due to poor tolerability, lack of efficacy, and failure to adhere to treatment. Clearly there is a medical need to develop effective, well-tolerated and safe preventive treatments for migraine.

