8.2. Exclusion Criteria

A subject who meets any of the following criteria will be excluded from the trial:

1. Receipt of any monoclonal antibody treatment, including ALD403 or any monoclonal antibody targeting the CGRP pathway (within or outside a clinical trial) within 6 months before screening.
2. Confounding and clinically significant pain syndromes (e.g. fibromyalgia, chronic low back pain, complex regional back syndrome, temporomandibular disorders).
3. Psychiatric conditions that are uncontrolled and/or untreated, including conditions that are not controlled for a minimum of 6 months prior to screening. Patients with a lifetime history of psychosis, mania, or dementia are excluded.
4. History or diagnosis of complicated migraine (ICHD-III beta version, 2013), chronic tension-type headache, hypnic headache, cluster headache, hemicrania continua, new daily persistent headache, or sporadic and familial hemiplegic migraine
5. Any use of approved devices, neuromodulation, neurostimulation or injectable therapy (trigger point injections, extracranial nerve blocks, facet joint for headache prophylaxis are prohibited 2 months prior to screening and during screening.
6. Any use of botulinum toxin for migraine or for any other medical/cosmetic reasons requiring injections in the head, face, or neck within 4 months prior to screening and during screening.
7. Any use of monoamine oxidase inhibitors (MAOIs), ketamine, methysergide, methylergonovine, or nimesulide within 3 months prior to screening.
8. Have present or previous malignancies, except:

- Squamous or basal skin cell carcinoma with excision, without evidence of recurrence, or
- Malignancy \geq 10 years since diagnosis/treatment without evidence of recurrence.

9. Subject has known history or evidence of cardiovascular disease, arteriosclerosis, cardiomyopathy, coronary artery disease, serious heart rhythm abnormalities, neurological disease, cerebrovascular disease, diabetes, Raynaud's disease, or life-threatening allergy (e.g., anaphylaxis). If questions arise, the Investigator should contact the Medical Monitor for guidance.

10. Primary hypertension that is uncontrolled or newly diagnosed (systolic BP of >139 mm Hg or diastolic BP of >89 mm Hg) at screening or secondary hypertension. Mild primary hypertension that is well-controlled for ≥ 6 months prior to screening is allowed.

11. Clinically significant abnormal ECG at screening or on Day 0.

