2.6.3 Interim Analyses

This study will include a formal interim analysis after all subjects have completed the primary treatment phase (i.e. approximately a year after the last subject enters the study).

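### The named cardiovascular and hepatic AESI terms leave out infarction, stroke and clinical liver events, and the list closes only at database lock, so AESI outputs can omit events that other safety tables show

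*SAP*

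**What the plan says.** SAP 3.6.2.1 builds each AESI category from a system organ class (SOC) combined with named preferred terms (PTs). Its opening sentence makes the list a minimum: "Adverse events of special interest include the following and additional PTs to be determined at time of database lock".

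The cardiovascular category draws on four classes:

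- Cardiac disorders: "PTs of Atrial fibrillation, Bradycardia, chest pressure, Palpitations, Sinus bradycardia, Sinus tachycardia and Tachycardia".
- Investigations: blood pressure, heart rate and ECG findings, beginning "PTs of Blood pressure increase, Blood pressure systolic increase, Elevated blood pressure, Heart rate increased, Heart rate decreased, Heart rate irregular, Electrocardiogram abnormal" and continuing with three more ECG terms.
- Nervous system disorders: "PTs of Seizure and Syncope".
- Vascular disorders: flushing, hot flush, hypertension, hypotension and ischemia.

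The hepatic category has six terms, all in Investigations: transaminase, bilirubin, liver enzyme and liver function test findings. The Hepatobiliary disorders class is not used.

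The same section then specifies four AESI outputs by SOC and PT: overall; by maximum severity, relationship and infusion interruption; those leading to discontinuation; and those assessed as serious.

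On timing, SAP 1.2 describes an open-label trial, and SAP 2.6.3 states: "This study will include a formal interim analysis after all subjects have completed the primary treatment phase". The SAP does not say which database lock closes the AESI list, or whether AESI outputs are produced at the interim.

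**The concern.** Long-term safety is the trial's primary objective, and a category titled as cardiovascular events will be read as the summary of cardiovascular safety. On the named terms alone, a hot flush enters it and an event coded to infarction or stroke does not. Similarly, a raised transaminase reported as an adverse event is a hepatic AESI, while hepatitis or jaundice is not.

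The plan's own text makes this area relevant. Protocol 5.2 says that CGRP, the drug's target, "is involved in the vasodilation, inflammatory cascade, and pain transmission associated with migraine". Protocol 8.2, exclusion 9, removes subjects with "evidence of cardiovascular disease, arteriosclerosis, cardiomyopathy, coronary artery disease" and also those with cerebrovascular or Raynaud's disease.

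The only route by which a missing term can enter is an addition at database lock. No selection rule, decision-maker or standard query is given. By then the sponsor of an open-label trial knows which events have occurred. A reader of the final tables could not tell whether a term was included on principle or because an event had been seen, nor whether an absent term was considered at all.

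**Working it through.** **The plan's own figure.** The AESI section states no number. The only related figure is the safety sample in SAP 1.3: 120 treated × 0.75 completing the primary phase = 90 subjects with one year of data. This reproduces, and nothing below changes it.

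**Count of named terms in SAP 3.6.2.1.**

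| Category | SOC | Named PTs | Content |
|---|---|---|---|
| Cardiovascular | Cardiac disorders | 7 | rhythm, rate, palpitations, chest pressure |
| Cardiovascular | Investigations | 10 | blood pressure, heart rate, ECG |
| Cardiovascular | Nervous system disorders | 2 | seizure, syncope |
| Cardiovascular | Vascular disorders | 5 | flushing, hot flush, blood pressure, ischemia |
| Hepatic | Investigations | 6 | laboratory findings |

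Cardiovascular total: 7 + 10 + 2 + 5 = 24. With the hepatic terms: 24 + 6 = 30.

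**Search of the 30 terms.** There is no match for infarction, angina, coronary disease, cardiac failure, cardiac arrest, stroke, cerebrovascular event, transient ischaemic attack (TIA), hepatitis, jaundice, liver injury or hepatic failure. The nearest entries are ischemia, a single PT within Vascular disorders, and the ECG Q-wave term.

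**Where an unlisted event would appear.**

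| Output | SAP section | Infarction, stroke or hepatitis shown? |
|---|---|---|
| All and drug-related treatment-emergent events (TEAEs) by SOC and PT | 3.6.1 | Yes |
| TEAEs by severity; by-subject listing | 3.6.1 | Yes |
| Serious events, listed and summarised | 3.6.2.2 | Yes, if serious |
| Deaths, listed | 3.6.2.3 | Yes, if fatal |
| AESIs by SOC and PT; serious AESIs | 3.6.2.1 | Not unless the term is added |
| AESIs by severity, relationship and infusion interruption combined | 3.6.2.1 | Not unless the term is added |
| AESIs leading to discontinuation, by SOC and PT | 3.6.2.1 | Not unless the term is added |

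The last two outputs have no counterpart for adverse events in general. For those, interruption and discontinuation appear only as overview counts in SAP 3.6.1. For the liver, SAP 3.6.3 plans laboratory shifts against the normal range, so no other SAP output groups clinical with laboratory liver events.

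**Illustration of scale.** Suppose one infarction and one stroke occur among n = 120, and neither subject has another event coded to a listed cardiovascular term. The count from the named terms is 0/120. The count from a list that includes both events is 2/120 = 1.7%. The exact (Clopper-Pearson) one-sided 95% upper limit is the p that solves P(X ≤ x | n, p) = 0.05:

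- x = 0: p = 1 − 0.05^(1/120) = 2.47%.
- x = 2: p = 5.15%.

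**Chance that the question arises.** The documents give no event rate. For an assumed per-subject risk p of any such event, the chance of at least one among 120 is 1 − (1 − p)^120:

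| Assumed p | Chance of at least one |
|---|---|
| 0.1% | 11% |
| 0.5% | 45% |
| 1% | 70% |
| 2% | 91% |

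**The case against.** The strongest reply is that the list is expressly open. A reader might infer that under this SAP an infarction or stroke cannot be a cardiovascular AESI. The opening sentence does not support that: the named terms are a floor, and an event stays out only if nobody adds its term at lock. This stands, and it limits the claim to what the outputs can do.

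A second inference would be that serious events could disappear from the report. They could not. The TEAE, SAE and death outputs carry them under their own terms, and an infarction or stroke would ordinarily meet the seriousness criteria in Protocol 11.1.2. A subject might also enter an AESI table through an accompanying ECG or transaminase event.

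Third, late additions do little statistical harm here. The trial has one arm, safety is summarised descriptively, no AESI hypothesis is tested, and the clause only adds terms, so it can raise counts but not lower them. This is largely right. What remains is the risk that a term is not added, and the reader's inability to see how the choice was made.

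Fourth, a reader might infer that ischaemia is what the AESI category exists to answer. No passage says so. Exclusion 9 also covers diabetes, neurological disease and life-threatening allergy, and Protocol 5.4 reports no specific toxicity of CGRP blockade to date. The mechanism and the exclusion make these events relevant; they do not rank them.

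Fifth, a mismatch between interim and final AESI counts is possible but not established, because the SAP does not say that AESI outputs belong to the interim.

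**Conclusion.** The point holds as a defect in the AESI summary. The named lists omit infarction, angina, heart failure, stroke, TIA and clinical liver events while including flushing and hot flush. The only planned remedy is an addition without a rule, made once open-label data are known. The AESI outputs can therefore be incomplete on the trial's primary objective, and the combined severity, relationship and interruption table and the PT-level discontinuation table have no substitute elsewhere.

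The size is modest. No event goes unreported, and the overall safety conclusion does not depend on the AESI tables. The contrast of 0/120 with 2/120 rests on two hypothetical events, no other listed term in those subjects, and no addition at lock. The SAP plans neither a category total nor a confidence limit, so 2.47% and 5.15% show scale and are not figures the report would print. The chances of 11% to 91% depend entirely on assumed risks of 0.1% to 2%. The change is worth making because it is specific and cheap.

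**What to change.** Amend SAP 3.6.2.1 before the interim data cut as follows.

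1. Fix the AESI term list at that point, and use the same list for any interim AESI outputs and for the final ones.
2. Add to the cardiovascular category ischaemic cardiac terms, heart failure, stroke and TIA, and arterial thrombotic or ischaemic terms. Taking every Cardiac disorders PT, with the relevant Nervous system and Vascular terms, is one way; an equivalent standardised MedDRA query is another.
3. Add clinical hepatobiliary terms to the hepatic category, for example every Hepatobiliary disorders PT or an equivalent query.
4. Replace the database-lock clause with a rule: any term added after the list is fixed is labelled post hoc, and counts are shown with and without it.

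The cost is SAP wording and a programming term list, with no new data collection. The downside is that broader categories give somewhat higher and less specific AESI counts.
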